At visit 4, participants will undergo spirometry to establish corticosteroid responsiveness. Participants will be randomized in a 1:1 allocation to: a) high dose vitamin D (100,000 IU load followed by 4,000 IU/day) plus low dose inhaled corticosteroid (ICS+D), or b) placebo vitamin D-like capsules plus low dose inhaled corticosteroid (ICS). All participants will receive open-label low dose inhaled corticosteroid and double-blind vitamin D capsules. At visit 5 U_{Ca}/U_{Creat} ratios will be monitored for hypervitaminosis D. At subsequent visits 6, 8 and 10, 25(OH)D and U_{Ca}/U_{Creat} ratios will be monitored for hypervitaminosis D (91). Treatment failure criteria will be thoroughly evaluated at each clinic visit, and participants will be asked to contact the clinical site between visits if they experience symptoms of treatment failure. During the treatment phase, the inhaled corticosteroid dose will be held stable for 12 weeks (Phase I), followed by a 50% inhaled corticosteroid reduction for 8 weeks (Phase IIa), and then a 75% inhaled corticosteroid reduction for the final 8 weeks (Phase IIb) (see below). A second methacholine bronchoprovocation will be performed in all participants at visit 6. A second sputum induction will be performed at visit 6 in 200 participants who provided an adequate sputum sample at visit 3. Throughout the treatment phase, participants will be assessed for colds and the WURSS-21 administered when a participant qets a cold. Exit interview will be conducted at visit 10.

B. Corticosteroid taper phases

At visit 6, participants will undergo tapering of their open-label inhaled corticosteroid dose if stability criteria are met (similar to those used in prior ACRN trial (80)). The purpose of corticosteroid tapering is to test the hypothesis that the addition of vitamin D may allow sparing of corticosteroid dose in participants with stable asthma. Furthermore, we will determine if the addition of vitamin D

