Although the safe tolerable upper intake level for vitamin D was set at 2,000 IU/day in 1997 by the National Academy of Sciences Institute of Medicine for adults and children greater than 1 year of age, (119) recent analyses indicate that this level could safely be updated to 10,000 IU/d, well above our chosen daily dose of 4,000 IU/day (110, 120, 121). As a benchmark, this same (4,000 IU/d) dose has been employed by other investigators in studies in related diseases such as atopic dermatitis (e.g. by the NIAID-funded Atopic Dermatitis and Vaccinia Immunization Network) (122) and an ongoing maternal supplementation study (123).

VIII. POWER ANALYSIS AND STATISTICAL METHODOLOGY

A. Power Analysis

In order to have 90% power to detect a hazard ratio of 1.8 from a Cox regression model (a reduction in treatment failure rate from 40% in the control group to approximately 24-25% in the intervention group during the randomized treatment period), a sample size of 200 participants per group is required. This calculation assumes an overall alpha level of 0.05, a 2-sided test, and 15% withdrawal (Power Analysis and Sample Size (PASS) Software 2008).

B. Statistical analysis methods

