The primary outcome of time from randomization to treatment failure will be evaluated during both the inhaled corticosteroid-stable and inhaled corticosteroid-taper phase of the trial. The pattern of treatment failure in the intervention and control groups will be visually described using the Kaplan-Meier method. The primary analysis will be a Cox proportional hazards regression model with time to treatment failure, from randomization, as the outcome and treatment group as the covariate of primary interest. Because we suspect that the hazard ratios to compare between the two groups may be different between the steroid-stable and steroid-taper phases of the trial, we will include taper status as a participant-specific time-dependent covariate as well as the interaction between taper status and treatment. If there is no clinically significant evidence of a treatment by taper interaction (defined below), then the interaction term will be removed from the model and the primary analysis p-value will correspond to the one-degree-of-freedom test of the treatment group main effect. If there is clinically significant evidence of a treatment by taper interaction, then there will be three Bonferroni adjusted p-values corresponding to the three one-degree-of-freedom contrasts for treatment effect within each level of the taper effect (stable, 50% taper and 75% taper).

The interaction effect will be evaluated by clinical, rather than statistical, significance because there is relatively low power for the standard two-degrees-of-freedom test of interaction. Clinical significance will be assessed by calculating the pair-wise ratios of the treatment effect hazard ratios for the three

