levels of the taper effect, and determining them to be clinically significantly different if the ratio of the hazard ratios does not fall within 0.8 to 1.25 (124). If only one of the three pairwise hazard ratio comparisons is clinically non-significant, then the taper levels corresponding to that comparison will be collapsed and the analysis will proceed as if there were only two taper levels. Under the null hypothesis of no treatment effect in any level of taper, this approach has a type-1 error rate of 5%. Under the alternative hypothesis of no interaction between treatment and taper, and with common treatment effect specified in section VIII.A., this approach has 90% power. Under the partially true alternative hypothesis of no treatment effect within two of the taper levels, but with treatment effect as specified above in the other taper level, this approach has a type-1 error rate no greater than 5% for the null taper levels and power of 84% for the non-null taper level. An adjusted model will be evaluated which will include the factors upon which the randomization was stratified: center, BMI (overweight/obese status), and race (African-American status). A secondary adjusted model will also consider the inclusion of the following baseline covariates that are of potential importance: gender, age, baseline 25(OH)D level, baseline sun exposure, baseline skin pigmentation level, FEV1 % predicted, OCS responsiveness, bronchodilator reversibility, and methacholine responsiveness (PC₂₀) measured on a continuous scale and transformed with the log₂ transformation. We will also evaluate the effect of seasonality on the study results by including season as a time-varying covariate in the adjusted model. The primary analysis will follow the intent-to-treat principle.

1

2

3

4

5

6

7

8

9

10

11

12

13

14

15

16

17

18

19

20

21

22

23

24

25

Vitamin D responder analysis: an exploratory analysis will be performed related to the primary hypothesis which will compare only those participants who reach sufficient levels of 25(OH)D in the treated group (≥30 ng/ml) to those participants in the control group, with respect to time to treatment failure as described above.

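### When exactly two of the three taper-level comparisons fall inside the 0.8 to 1.25 band, the primary analysis drops to three unpooled Bonferroni tests, the weakest branch of the rule

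*Protocol*

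**What the plan says.** Section VIII.B builds the primary analysis on a Cox model with treatment, taper status (stable, 50% taper, 75% taper) and their interaction. The three treatment hazard ratios are compared pairwise, and a pair counts as clinically different when its ratio lies outside 0.8 to 1.25. Three instructions follow.

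- "If there is no clinically significant evidence of a treatment by taper interaction", the interaction term is dropped and one one-degree-of-freedom treatment test decides.
- "If there is clinically significant evidence of a treatment by taper interaction, then there will be three Bonferroni adjusted p-values", one for each taper level.
- "If only one of the three pairwise hazard ratio comparisons is clinically non-significant, then the taper levels corresponding to that comparison will be collapsed"; two levels then remain to be tested.

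The section claims a type-1 error rate of 5% and, under a common effect, 90% power for this whole approach. Section VIII.A sets the design effect: "In order to have 90% power to detect a hazard ratio of 1.8 from a Cox regression model".

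**The concern.** The number of pairs inside the band can be 0, 1, 2 or 3. The collapsing sentence serves only the case of 1. With 2 inside, the middle level is close to both others while the two extremes differ by more than 1.25. One clinically different pair remains, so the second instruction governs and all three levels are tested separately.

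Strictness therefore moves in the wrong direction between 1 and 2 inside: an additional similar pair removes the pooling and lowers the threshold from 0.025 to 0.0167. At stake is the primary verdict. A benefit present at all three levels can fail in this branch, while a less even result with weaker overall evidence succeeds in the neighbouring one.

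**Working it through.** **Inputs.** From section VIII.A: hazard ratio 1.8 (control against vitamin D); "a reduction in treatment failure rate from 40% in the control group to approximately 24-25% in the intervention group"; "a sample size of 200 participants per group is required"; "This calculation assumes an overall alpha level of 0.05, a 2-sided test, and 15% withdrawal". Allocation is 1:1 (section VI.A). The protocol gives no split of events over the taper levels, so the splits below are assumptions.

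**Reproducing the stated power of the single test.** A 40% control rate and a hazard ratio of 1.8 give 1 − 0.60^(1/1.8) = 24.7% on vitamin D. Events without withdrawal: 200 × (0.40 + 0.247) = 129. Counting the 15% withdrawn at half exposure: 129.4 × (1 − 0.15/2) = 120. Then z = ln(1.8) × √120 / 2 = 3.22, and power = Φ(3.22 − 1.96) = 89.6%. This agrees with the stated 90%.

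**The four branches as written.**

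| Pairs inside band | Tests | Threshold per test |
|---|---|---|
| 3 | one, all levels pooled | 0.05 |
| 2 | three, no pooling | 0.0167 |
| 1 | two, one on merged levels | 0.025 |
| 0 | three, no pooling | 0.0167 |

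**Worked example.** Take 40 events per level and z = |ln HR| / (2/√40), with hazard ratios as vitamin D against placebo.

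- 0.50 / 0.60 / 0.65: ratios 1.20, 1.08 and 1.30, so two inside. Level p-values are 0.028, 0.106 and 0.173; the smallest times 3 is 0.085. It fails, although the pooled one-df p is 0.003.
- 0.50 / 0.55 / 0.90: ratios 1.10, 1.64 and 1.80, so one inside. The first two levels merge: z = 0.6455 / (2/√80) = 2.89, p = 0.0039, doubled 0.008. It succeeds for the merged levels, although the pooled one-df p is weaker (0.011).

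**Simulation.** One million trials per scenario; each level's log hazard ratio is normal with variance 4/(events in that level); common hazard ratio 1.8; 120 events; success means that any adjusted test rejects.

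| Event split (%) | Frequency of 2 inside | Power with 0 / 1 / 2 / 3 inside | Overall power as written |
|---|---|---|---|
| equal | 10.9% | 88 / 87 / 45 / 90% | 83.0% |
| 20/40/40 | 10.2% | 83 / 86 / 49 / 90% | 81.9% |
| 43/28.5/28.5 | 10.6% | 86 / 86 / 45 / 90% | 82.2% |
| 20/30/50 | 10.0% | 82 / 85 / 48 / 90% | 81.3% |
| 60/20/20 | 9.1% | 79 / 84 / 55 / 90% | 80.6% |

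The two-inside branch is the weakest at every split. The last split sits badly with section X.D, which expects most failures during tapering; without it the ranges are 10% to 11% of trials and 45% to 49% power.

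**Under no effect** (147 events; 400 × 0.40 × 0.925 is about 148), the chance of any false rejection by the whole rule is 8.2% to 8.9% over the same splits.

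**The case against.** Several points on the other side stand.

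- A reader might infer that the rule generally punishes consistency. It does not. Three pairs inside are pooled and tested at 0.05, and none inside meets the same 0.0167 as two inside. The reversal is between two inside and one inside only.
- Two inside does not always mean less heterogeneity. The extremes can differ by up to 1.25 × 1.25 = 1.56. Hazard ratios 0.40 / 0.49 / 0.59 (two inside) span 1.48, while 0.50 / 0.51 / 0.64 (one inside) span 1.28. Less spread holds on average: at the equal split the median span is 1.33 with two inside and 1.67 with one, and about a third of one-inside trials span less than 1.56.
- A reader might also infer that the plan names no primary contrast for this case. It does: one pair outside the band is a clinically significant difference by the section's own definition, so the three-test default applies. That default even has a rationale, since with two pairs inside it is unclear which to merge.
- The power gap is partly an artefact of choosing the branch from the data. Under no effect at the equal split, the one-inside branch rejects about 10% of the time and the none-inside branch about 15%, against 0.1% with two inside. The comparison branch is inflated, not simply better.

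None of this removes the gap in the collapsing sentence or the low power of the branch to which it leads.

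**Conclusion.** The concern holds as a narrow defect of the decision rule. A possible pattern is left out of the collapsing sentence and falls to the least powerful branch: 9% to 11% of trials under the design effect, with 45% to 55% power there. The rule is determinate, so this is a badly ordered step and not an undefined analysis.

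The figures rest on about 120 events, a common hazard ratio of 1.8, a normal approximation with independent level estimates, and assumed event splits. The direction was the same at every split tried. The effect on overall power is modest, a few points, but it falls on the primary verdict and is cheap to remove.

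**What to change.** Replace the collapsing sentence in section VIII.B with a rule for both mixed patterns, fixed before unblinding:

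> If one or two of the three pairwise ratios lie within 0.8 to 1.25, merge the two taper levels whose ratio is closest to 1 and make two Bonferroni-adjusted tests, one for the merged level and one for the remaining level.

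The one-inside case is unchanged, because its only inside pair is also the closest. In the two-inside branch, power rises to about 70% to 75%. Overall power rises by 2 to 3 points; at the equal split, 10.9% × (70.4 − 45.2) = 2.7 points, from 83.0% to 85.7%.

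**Cost.** One sentence; no participants or data. The chance of any false rejection rises by 0.1 to 0.2 points (8.9% to 9.1% at the equal split). It is already well above the 5% that the section states for the whole rule; that figure needs restating separately.

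**Limits.** The change does not rescue every such trial. In the 0.50 / 0.60 / 0.65 example the closest pair is 0.60 and 0.65, and the two adjusted p-values become 0.057 (remaining level) and 0.070 (merged), still short of 0.05. With hazard ratios 1.60 / 1.80 / 2.04 (control against vitamin D, about 41 events per level), the smallest adjusted p moves from 0.069 to 0.034.

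Pooling all three levels with a one-df test would recover more power (87.8% overall at the equal split). It is not recommended: it merges levels that the protocol itself calls clinically different and takes the false-rejection rate to about 9.6%.

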Participants who experience two treatment failures during the run-in period or OCS response period (one each during two separate enrollments) will not be allowed to participate in the study further. This will enrich the study population for individuals who are likely to remain stable during the stable inhaled corticosteroid dose phase (Phase I) with the bulk of treatment failures likely to occur during the inhaled corticosteroid tapering phase (Phases IIa and IIb).

For participants who meet criteria for treatment failure during the post-randomization phases of the study, the dose of inhaled corticosteroid will be doubled and continued for 7 days. For treatment failures occurring during Phase I, the dose will be twice the inhaled corticosteroid stable dose. For treatment failures occurring during Phase II, the dose will be increased to the dose the participant was receiving prior to initiation of the most recent steroid taper (i.e. returned either to Phase I or Phase IIa dosing, as appropriate). If, after 7 days, the treatment failure episode is clinically-resolved, the corticosteroid stable dose (for treatment failures during Phase I) or pre-failure tapering dose (for treatment failures during Phase II) of inhaled corticosteroid will be resumed and study visits will continue as per protocol. If an exacerbation or second treatment failure occurs during the post-randomization phases of the study, no further inhaled corticosteroid dose tapering will be attempted.

For participants who experience a treatment failure event that also meets the criteria for a significant asthma exacerbation, dosing of inhaled corticosteroid depends on the phase in which the

event occurred. If the exacerbation occurs during Phase I, the dose of inhaled corticosteroid will be doubled (to 200% of the inhaled corticosteroid stable dose) for 7 days. If, after 7 days, the event is clinically-resolved, the dose will be reduced back to the corticosteroid stable dose for the remainder of the study, and visits will continue as per protocol. If the exacerbation occurs during Phase II, the dose of inhaled corticosteroid will be increased to the corticosteroid stable dose and maintained for the remainder of the study; no additional dosing tapers will be attempted. Additional treatment for exacerbations is at the treating physician's discretion (see Section 2 below).

1. Treatment Failure Rescue Algorithm

Home Care

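### The 84% power stated for a single effective taper level is not supported by the design: it would need practically all of the trial's expected first failures to fall in that level

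*Protocol*

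**What the plan says.** Section VIII.A sizes the whole trial: "In order to have 90% power to detect a hazard ratio of 1.8 from a Cox regression model", described as "a reduction in treatment failure rate from 40% in the control group to approximately 24-25% in the intervention group" over the randomized treatment period. It concludes that "a sample size of 200 participants per group is required" and adds: "This calculation assumes an overall alpha level of 0.05, a 2-sided test, and 15% withdrawal".

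Section VIII.B makes time from randomization to treatment failure the primary outcome, and its comment on tapering treats this as the first failure. If the treatment-by-taper interaction is judged clinically significant (a ratio of hazard ratios outside 0.8 to 1.25), the three taper levels (stable, 50%, 75%) are tested separately with Bonferroni adjustment. If exactly one pairwise comparison is non-significant, those two levels are merged and two tests remain. For the case where the VIII.A effect exists in one level only, VIII.B claims a "type-1 error rate no greater than 5% for the null taper levels and power of 84% for the non-null taper level".

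The protocol gives no expected number or share of failures by level. Section X.D says only that the enrolment rules should leave a population stable in Phase I, "with the bulk of treatment failures likely to occur during the inhaled corticosteroid tapering phase", meaning IIa and IIb, which are two separate levels in the analysis.

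**The concern.** Each participant contributes at most one first failure, so the failures that give the whole trial 90% power have to be shared among three levels. A test confined to one level uses only that level's share, at a stricter alpha. A fall from 90% to only 84% looks too small for that.

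This matters because VIII.B itself suspects that the treatment effect differs between the stable and taper phases, so the one-level scenario is one the protocol anticipates. A reader who trusts 84% may take a non-significant result in one level as good evidence of no effect there, when the chance of detecting the design effect may have been below one half.

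**Working it through.** **Inputs.** From VIII.A: hazard ratio (HR) 1.8, 40% control failure, 200 per group, two-sided 0.05, 15% withdrawal. From VI.A: 1:1 allocation and phases of 12, 8 and 8 weeks. From VIII.B: the decision rule described above.

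**Step 1: the whole-trial figure reproduces.**
- Intervention failure: 1 - 0.6^(1/1.8) = 24.7%, which agrees with VIII.A.
- Events needed (Schoenfeld): 4(z_alpha + z_power)^2 / (ln 1.8)^2 = 4(1.960 + 1.282)^2 / 0.3455 = 122.
- Events expected without withdrawal: 200 x (0.400 + 0.247) = 129.
- Events expected with 15% exponential withdrawal: the chance of an observed failure is h/(h+w) x [1 - exp(-(h+w))], with w = 0.1625 and h = 0.5108 (control) or 0.2838 (intervention). This gives 0.372 and 0.229, so 200 x 0.601 = 120.
- Events expected if withdrawals contribute nothing (170 per arm): 110.
- Power: 92%, 90% and 87% respectively. The 90% is sound.

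**Step 2: failures needed inside one level for 84%** (z_power = 0.9945).

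| Alpha for the level | Schoenfeld | Freedman |
|---|---|---|
| 0.05/3 | 4(2.394 + 0.9945)^2 / 0.3455 = 133 | 141 |
| 0.05/2 | 4(2.241 + 0.9945)^2 / 0.3455 = 121 | 129 |
| 0.05, unadjusted | 4(1.960 + 0.9945)^2 / 0.3455 = 101 | 107 |

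**Step 3: where 84% comes back.** With the whole trial's 90% information in one level, tested at 0.05/2: Phi(1.960 + 1.282 - 2.241) = 84.1%. With the expected 120 events, 83.6%. At 0.05/3 the same 120 events give 79.5%.

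**Step 4: power with a share of 120 failures.** Power = Phi(sqrt(d) x ln 1.8 / 2 - z_alpha).

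| Failures in the level | alpha 0.05/3 | alpha 0.05/2 |
|---|---|---|
| 30 (25%) | 22% | 26% |
| 40 (one third) | 30% | 35% |
| 60 (50%) | 45% | 51% |
| 72 (60%) | 54% | 60% |

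**Step 5: the full rule under the one-level alternative.** Piecewise-exponential simulation of the 0.8-1.25 screen, merging and Bonferroni, with 15% exponential withdrawal and 20,000 runs per scenario. Everyone tapers on schedule. Three tests are used when exactly two pairs are non-significant, a case the protocol does not address. The splits are assumed shares of the control-group hazard. Any rejection covering the effective level counts as success, including one for a merged or pooled level, which favours the protocol.

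| Split (I / IIa / IIb) | Trial failures | Failures in effective level (I, IIa, IIb) | Power (I, IIa, IIb) |
|---|---|---|---|
| Equal | 138-139 | 48, 38, 31 | 40%, 31%, 24% |
| By phase length | 136-142 | 60, 31, 26 | 51%, 24%, 19% |
| 20/40/40 | 135-140 | 29, 48, 37 | 22%, 40%, 30% |

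If only tests of the effective level on its own count, these powers fall to 16-41%. A level with 5% of the hazard has about 1% power. With 80-90% of the hazard in the effective level, power is about 65-72% if that level is IIb and about 75-78% if it is Phase I. No split tested reached 84%.

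**Step 6: errors in the null levels.** For the three splits in the table, counting a rejection of a merged or pooled level against every level in it, the rate is about 3-8% for each null level and about 6-12% for at least one of the two.

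**The case against.** The strongest defence is that 84% is a real calculation resting on an unstated assumption. VIII.B puts the effect as specified in VIII.A into one level. If the two null levels merge, two tests at 0.05/2 remain, and full design information then gives 84%. That explains the likely origin, and it means a reader should not call the figure impossible: it is attainable if practically all failures fall in the effective level. It does not rescue the figure, because VIII.A ties the 40% and 24-25% to the whole randomized period, and X.D places most failures in two levels together, not in one.

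A second objection is that about 120 failures is the total under a common effect. With two levels null the intervention arm fails more often, and the total rises to about 135-142 for the splits in the table. This is correct, but the extra failures fall in the null levels and add nothing to the test of the effective one.

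Third, a reader might take 20-50% as the true power. The documents do not support that: they give no split, and lopsided splits fall well outside the range.

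Fourth, a reader might conclude that the 5% ceiling simply fails. That is also too strong. The sentence does not say per level or across both null levels, several per-level rates are at or below 5%, and a pooled level containing the effective one is not strictly null, so calling its rejection a type-1 error is a matter of definition. What stands is that a rejection then carries over to a level with no effect.

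Finally, the 84% sizes nothing. The sample size rests on the 90% calculation, which reproduces.

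**Conclusion.** The point holds for the 84%. At HR 1.8 it needs 121 to 133 first failures inside one level, against about 120 expected in the whole trial under a common effect and about 135-142 under the one-level alternative with even or moderate splits, of which only about 26 to 60 fall in the effective level. Under those assumed splits the full rule has roughly 20-50% power. This range depends on the assumed split, proportional hazards within each level, exponential withdrawal and tapering on schedule. It is lower in a sparse level and higher, though still short of 84%, in a dominant one.

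The 5% statement is under-defined rather than shown to be wrong. The 90% overall power and the 200 per group are not in question.

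**What to change.** In VIII.B:

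1. Delete the 84%, or replace it with power recomputed for the full decision rule under an explicitly stated split of failures across the three levels, preferably over a range of splits.
2. Present the level-specific contrasts as hazard ratios with 95% confidence intervals, and state that a non-significant result in one level is not evidence of no effect there.
3. Say whether the 5% limit applies to each null level or to both together, and note that when a null level is merged or pooled with the effective one, a rejection carries over to it. Give the resulting rates under the same stated split.

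The cost is wording and one simulation. No participants, visits or endpoints change. The stated power for level-specific effects becomes less favourable.
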